## 10.1. Master Plan of Analysis

The primary goal of the statistical analyses to be performed as part of this study will be the identification of factors associated with the development of autoimmunity and T1DM. In order to accomplish this, we will employ two different types of analysis, depending on the nature of the factor being studied.

- For those factors whose values will be known to us without additional costs, we will perform log rank tests and Cox Proportional Hazards Regressions. For these analyses, the dependent variable will be the age at which the event being studied (development of autoimmunity or diagnosis of T1DM) occurred. Those not achieving the event when the analyses are being performed and those lost to follow-up without achieving the event will be considered censored as of the date last known to be event-free. The log rank test will be used to study factors with a few discrete values. For example:
  - (a) Family History
  - (b) Haplotype
  - (c) Breast-feeding

For factors with continuous values, we will test for conformity of those values with the proportional hazards assumption by examining the significance of the interaction of the time variable (treated as a time-dependent covariate) with the factor. If there is an indication of a non-zero interaction coefficient, (p < 0.10) we will dichotomize the variable and use the log rank test instead of proportional hazards regression. Otherwise, we will use proportional hazards regression to test for significance at the .01 significance level. The following are examples of factors to be studied in this manner:

- (a) Amounts of certain nutrients consumed
- (b) Duration of breast feeding
- (c) Maternal anxiety and depression as measured by the State Trait Anxiety Inventory and the Edinburgh Postnatal Depression Scale

Proportional hazards regression will be used in both a univariate and multivariate manner and reported both ways. For each factor studied, estimated hazard ratios and their 95% confidence intervals will be computed. When a set of factors that predict conversion to T1DM or autoimmunity are determined as described above, we will compute estimated "survival" curves for subjects having specific factor profiles.

2) For those factors whose determination is costly we will employ a nested casecontrol design. At the time at which a cohort subject converts to autoimmunity or

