T1DM (referred to as cases) we will randomly select k subjects who did not convert to autoimmunity or T1DM (controls). The sampling for the selection of matched controls is based upon incidence density sampling which allows the comparison of cases with a subset of the cohort at risk of being cases at the time when each case occurs, or equivalently matches cases and controls for the duration of follow-up. Since controls selected in this way may become cases over time, we will employ over sampling of controls and may select different controls at different points in time.

We will then compare these cases to controls as a matched case control study using conditional logistic regression. The value of k will be determined in order to have at least 80% power based on tables 14 -16, taking into consideration the number of cases available for the analysis. Thus, these expensive determinations will be made only on the cases and their chosen matched controls. Matching will be based on HLA type, study center, duration of follow-up, and completeness of data including serial biological samples. Every effort will be made to use the same controls for multiple case-control studies. This will allow inclusion of all key exposures simultaneously in the analytical model and exploration of confounding, effect modification, and interactions between exposures. The standard set of controls will include only those with complete data/samples for all components of the protocol. Since we do not need to have the same number of controls for each case, we will strive for an average of k controls for each case – not exactly k for each case. These analyses will also be performed in both a univariate and multivariate fashion. Odds ratios for each factor will be computed, as will their 95% confidence intervals. ROC curves for sensitivity vs. 1 specificity based on combinations of these factors will be computed. Here sensitivity refers to the ability of the factors to predict conversion to the study endpoint among those who do convert and specificity refers to ability to predict conversion free survival among those who are.

Similar analyses will be performed for development of autoimmunity and T1DM. Since the cases for T1DM will be a subset of the cases for autoimmunity, we will attempt to use the same controls. However, since there will be fewer cases, additional controls will be needed. Again, the (average) number of controls per case will be guided by tables 14 - 16.

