Ov	er 5 years	General Population	on FDF	ł			
Enroll		7,013	788				
Cases - autoantibodies by age 6		281 (4%)	105 (13.	3%)			
Cases - T1DM by age 15		281 (4%)	105 (13.	3%)			

Based on submissions by the participating institutions, we expect to be able to enroll 7,013 subjects from the general population and 788 relatives in five years. Those from the general population and the relatives are expected to have about 4% and 13.3% autoimmune conversion at 6 years respectively. Tables 6-13 below give the power for a Log Rank Test at a two-sided 0.01 significance level for the general population subjects, the relatives, and the pooled sample accrued over 5 years with 15 years of post-accrual follow-up for dichotomous pre-birth triggers of frequencies 1%, 5%, 10%, and 20% and hazard ratios of 1.5 and 2.0 and losses to follow-up at rates of 0%, 2%, 5%, and 10% per year. These calculations are based on the method of Lakatos (Lakatos, 1998) using a computer program described by Cantor (Cantor, 2003).

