## Table 6: Power for Prospective Study- General Population –Diabetes End Point, Alpha = .01, N = 7013, 5 Years Accrual, Follow-Up to age 15, 4% Conversion among Unexposed at 15 Years

Exposed %	LTFU %/year	Power ( HR = 1.5)	Power ( HR = 2.0 )
1	0	0.05	0.21
5	0	0.26	0.89
10	0	0.52	0.99
20	0	0.81	0.99
1	2	0.04	0.17
5	2	0.21	0.82
10	2	0.44	0.98
20	2	0.72	0.99
1	5	0.03	0.13
5	5	0.16	0.71
10	5	0.34	0.95
20	5	0.59	0.99
1	10	0.03	0.09
10	10	0.23	0.83
20	10	0.42	0.98
5 10	10 10	0.11 0.23	0.52 0.83

Table 7: Power for Prospective Study- Relatives – Diabetes End Point Alpha = .01, N = 788, 5 Years Accrual, Follow-Up to age 15, 13.3% Conversion among Unexposed at 15 Years

Exposed %	LTFU %/year	Power (HR = 1.5)	Power ( HR = 2.0)
1	0	0.02	0.06
5	0	0.07	0.33
10	0	0.14	0.62
20	0	0.27	0.87
1	2	0.02	0.05
5	2	0.06	0.27
10	2	0.12	0.53
20	2	0.22	0.80
1	5	0.02	0.04
5	5	0.05	0.21
10	5	0.09	0.42
20	5	0.17	0.68
1	10	0.02	0.03
5			0.03
	10	0.04	
10	10	0.06	0.29
20	10	0.11	0.51

Table 8: Power for Prospective Study- Pooled Sample – Diabetes End Point,
Alpha = $.01$ , N = 7801, 5 Years Accrual, Follow-Up to age 15,
5.5% Conversion among Unexposed at 15 Years

$\begin{array}{c ccccccccccccccccccccccccccccccccccc$	Exposed %	LTFU %/year	Power ( HR = 1.5)	Power ( HR = 2.0 )
$ \begin{array}{c ccccccccccccccccccccccccccccccccccc$				
$\begin{array}{c ccccccccccccccccccccccccccccccccccc$	1	0	0.07	0.35
$\begin{array}{c ccccccccccccccccccccccccccccccccccc$	5	0	0.43	0.98
$\begin{array}{c ccccccccccccccccccccccccccccccccccc$	10	0	0.75	0.99
$ \begin{array}{cccccccccccccccccccccccccccccccccccc$	20	0	0.95	0.99
$\begin{array}{c ccccccccccccccccccccccccccccccccccc$	1	2	0.06	0.29
$\begin{array}{c ccccccccccccccccccccccccccccccccccc$	5	2	0.35	0.96
$\begin{array}{c ccccccccccccccccccccccccccccccccccc$	10	2	0.66	0.99
$ \begin{array}{cccccccccccccccccccccccccccccccccccc$	20	2	0.91	0.99
$ \begin{array}{cccccccccccccccccccccccccccccccccccc$				
$\begin{array}{cccccccccccccccccccccccccccccccccccc$		5	0.05	0.22
20         5         0.82         0.99           1         10         0.04         0.14           5         10         0.18         0.75           10         10         0.37         0.96	5	5	0.27	0.90
1         10         0.04         0.14           5         10         0.18         0.75           10         10         0.37         0.96	10		0.54	0.99
5100.180.7510100.370.96	20	5	0.82	0.99

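### Profile survival curves and ROC curves come from the same children used to choose and fit the factors, with no optimism correction specified; as written they overstate separation, mainly where power is low

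*Protocol*

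**What the plan says.** Section 10.1 of the protocol describes two analyses.

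**Prospective part.** Discrete factors go to the log rank test. Continuous factors are first checked for proportional hazards: "If there is an indication of a non-zero interaction coefficient, (p < 0.10) we will dichotomize the variable and use the log rank test". For those that pass the check: "Otherwise, we will use proportional hazards regression to test for significance at the .01 significance level". For log rank factors, section 10.1 gives no level; the 0.01 level appears only in the power section (10.3): "Tables 6-13 below give the power for a Log Rank Test at a two-sided 0.01 significance level". Cox models are reported in two forms: "Proportional hazards regression will be used in both a univariate and multivariate manner and reported both ways". Estimates are not confined to significant factors: "For each factor studied, estimated hazard ratios and their 95% confidence intervals will be computed". The curves come next: "When a set of factors that predict conversion to T1DM or autoimmunity are determined as described above, we will compute estimated" survival curves for subjects with specific factor profiles. The text thus ties the curves to the set of factors found by testing.

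**Nested case-control part.** After univariate and multivariate conditional logistic regression: "ROC curves for sensitivity vs. 1 specificity based on combinations of these factors will be computed". Sensitivity and specificity are described there as ability to predict conversion and conversion-free survival. No p-value rule is given for which factors enter these combinations; in this part, alpha of .01 appears only in power Tables 14 to 16.

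The protocol names no hold-out sample, cross-validation, bootstrap correction or shrinkage for either output.

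**The concern.** Two known effects are at work.

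- **Selection.** An estimate that has passed a strict threshold is, on average, further from the null than the truth. The gap widens as power falls. A curve drawn from factors chosen this way inherits it.
- **Same-data evaluation.** An ROC curve computed on the children whose data fitted the model gives apparent accuracy, which exceeds accuracy in new children even if no p-value screen was used. A screen adds to the gap.

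Section 10.1 calls its list of prospective analyses non-exhaustive, so the pool of candidate factors is open-ended. At stake is how a reader would take the curves and the AUC: as what the factors can do in other children, when they show what the factors did in this sample.

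**Working it through.** **1. Reproduce the plan's own power.** Inputs from Table 6: N = 7,013, 4% conversion among the unexposed at 15 years, two-sided 0.01, no loss to follow-up. Lakatos log rank power with exponential hazards, 5 years of uniform accrual and 15 further years gives, at 1/5/10/20% exposure:

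- HR 1.5: 0.05/0.26/0.52/0.80 (printed 0.05/0.26/0.52/0.81)
- HR 2.0: 0.21/0.89/0.99/1.00 (printed 0.21/0.89/0.99/0.99)

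The printed powers can therefore be used as they stand.

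**2. Mean estimate among factors that pass at 0.01.** With b = ln(HR), printed power w and critical value 2.576:

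- se = b / (z_w + 2.576)
- c = 2.576 − b/se = −z_w
- E[estimate | significant] = b + se × φ(c) / (1 − Φ(c))

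Worked case, HR 1.5 with 5% exposed: b = 0.4055, w = 0.26, z_w = −0.643, se = 0.4055/1.932 = 0.210, c = 0.643, φ/(1 − Φ) = 1.248. The mean is 0.4055 + 0.210 × 1.248 = 0.667, so HR = 1.95. On the log scale the inflation is 0.667/0.4055 = 1.65. Counting selections in the wrong direction changes none of the values below at the precision shown.

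| Source in section 10.3 | True HR | Exposed | Loss per year | Printed power | Mean HR if significant | Log-scale factor |
|---|---|---|---|---|---|---|
| Table 6 (diabetes, general population) | 1.5 | 5% | 0% | 0.26 | 1.95 | 1.65 |
| Table 6 | 1.5 | 10% | 0% | 0.52 | 1.69 | 1.29 |
| Table 6 | 1.5 | 20% | 0% | 0.81 | 1.56 | 1.10 |
| Table 6 | 1.5 | 10% | 5% | 0.34 | 1.84 | 1.50 |
| Table 6 | 2.0 | 5% | 0% | 0.89 | 2.08 | 1.06 |
| Table 6 | 2.0 | 10% | 0% | 0.99 | 2.01 | 1.01 |
| Table 6 | 2.0 | 5% | 10% | 0.52 | 2.45 | 1.29 |
| Table 8 (diabetes, pooled) | 1.5 | 10% | 0% | 0.75 | 1.58 | 1.13 |
| Table 9 (autoantibodies, general population) | 1.5 | 10% | 0% | 0.93 | 1.52 | 1.04 |

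**3. Chance selections.** The number of candidates is not stated, so 20, 50 and 100 independent candidates are assumed. If none has an effect, the chance that at least one passes is 1 − 0.99^m = 0.18, 0.39 and 0.63.

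**4. AUC optimism, by simulation.** Assumptions: independent binary factors with 10% exposure, five true factors, univariate selection at p < 0.01, multivariable logistic refit, and apparent AUC compared with AUC in new data. The 0.01 screen is an assumption for the case-control part. Matching is not modelled, and the cohort runs approximate Cox by logistic regression.

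- 380 cases and 760 controls, OR 1.5, 20/50/100 candidates: apparent 0.560/0.563/0.571, new data 0.535/0.533/0.529, optimism 0.024/0.029/0.041, median calibration slope 0.62/0.58/0.40.
- Same numbers, OR 2.0, 50/100 candidates: apparent 0.642/0.644, new data 0.623/0.621, optimism 0.019/0.023, slope 0.87/0.84.
- 460 cases and 1,380 controls: optimism 0.019 to 0.033 at OR 1.5 and 0.012 to 0.017 at OR 2.0.
- Cohort of 7,801 with 386 events: optimism 0.016 to 0.035 at HR 1.5 and 0.012 to 0.017 at HR 2.0.

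With 380 cases and OR 1.5, optimism is 0.024/0.060 = 0.40 to 0.041/0.071 = 0.58 of the apparent AUC above 0.5. At OR 2.0 it is 0.019/0.142 = 0.13 to 0.023/0.144 = 0.16.

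**The case against.** The strongest reply is that the protocol does not say the coefficients are unpenalised or that validation is excluded. Such detail often sits in a statistical analysis plan, which was not available here. That stands against any reading that inflation is built in by design: the text supports only that no correction is specified. It does not dispose of the point, because section 10.1 does fix the order, testing first and curves from the resulting set, and carrying that out literally gives optimistic output.

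Other objections also narrow the point:

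- **One screen feeding both outputs.** A reader might infer that factors are screened at 0.01 and then fed into both the curves and the ROC. The documents do not support this. The 0.01 rule in section 10.1 covers continuous Cox factors in the prospective part, and the case-control part states no screen. For the ROC, the point rests on fitting and judging on the same data.
- **The design target.** Sections 10.2 and 10.3 aim at hazard ratios of about 2. At that size, with 5% or more exposed and no loss, inflation is slight. For autoantibodies, the first primary outcome, it is slight even at 1.5 with 10% exposed.
- **Compounding across factors.** A reader might multiply the inflation over several rare factors to get a dramatic profile. Three independent 5% exposures would coincide in 0.05³ × 7,013 = 0.9 children, so that is not a realistic illustration.
- **Matching.** Controls are matched on HLA type and center, which removes the discrimination those factors would add. The net direction of error, if the matched ROC were read as accuracy in the whole cohort, is therefore uncertain.
- **Purpose.** The stated goal is to identify associated factors. Section 10.2.3 describes the study as hypothesis forming and promises cautious interpretation, in the context of interim analyses and type 1 error. No section uses these curves to inform families of risk.
- **Full reporting.** Hazard ratios and intervals for every factor studied help the reader, but they do not correct the curves.

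**Conclusion.** The concern holds in a limited form. As written, with no correction specified, the profile curves will overstate risk separation and the ROC curves will overstate discrimination relative to new children sampled in the same way.

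For factors passing the 0.01 test, the overstatement is small where power is high: a hazard ratio of 2.0 appears as 2.01 to 2.08 at power 0.89 to 0.99. It is material where power is low: 1.5 appears as about 1.69 at power 0.52 and 1.95 at power 0.26. Loss to follow-up moves some hazard ratios of 2.0 into the low-power range as well. AUC optimism is about 0.01 to 0.04, a modest absolute amount but a large share of the discrimination when effects are near 1.5.

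The hazard ratio figures rest on the printed powers and a normal approximation. The AUC figures rest on assumed candidate counts, exposure and independence. This is a cheap improvement to the analysis, not an error that invalidates the tests of association.

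**What to change.** Add a paragraph to the analysis plan covering four points:

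1. Repeat the whole procedure, factor selection and model fitting included, inside bootstrap or cross-validation samples. In the case-control part, resample whole matched sets.
2. Report the optimism-corrected AUC or c-index beside the apparent one.
3. Show the profile curves with a version shrunken by the calibration slope, or label them plainly as apparent.
4. State how factors are chosen for the ROC combinations, so that the resampling can repeat that step.

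The cost is computing time and somewhat less favourable accuracy figures. No new data are needed, and the tests of association are unchanged.

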Several studies have shown that gestational events contribute to an increased risk of T1DM. The most prominent example is exposure to rubella during pregnancy. About 20 % of children born with congenital rubella develop type 1 diabetes (Menser et al., 1978; Ginsberg-Fellner et al., 1985). More recent studies have shown an increased risk for childhood T1DM if the mother has had an infection with enteroviruses during pregnancy (Dahlquist et al., 1995; Hyoty et al. 1995). Other events during pregnancy or at delivery such as preeclampsia also confer T1DM risk (Dahlquist et al., 1989; Jones et al., 1998; Dahlquist et al., 1999). High birth weight and children born large for gestational age have a higher risk of T1DM than controls (Dahlquist et al., 1996; Stene et al., 2001). Neither of these phenomena are understood and it may be necessary to analyze them in relation to genetic incompatibilities between mother and child such as non-inherited maternal haplotypes (Kockum et al., 1994; Hampe et al., 2002) or blood incompatibility such as ABO-incompatibility was related to an increased risk for T1DM (Dahlquist and Kallen, 1992).

The risk that a child will develop T1DM is increased when born to a T1DM mother compared to the general population. However, the risk of the child developing the disease is higher when born to a T1DM father. Thorough studies have been carried out in the BABYDIAB project to investigate neonatal factors that are associated with the appearance of islet autoantibodies and sometimes T1DM during postnatal follow-up ([name] et al., 1999). However, little is known about the consequences for islet autoimmunity or T1DM development when born to a mother with subclinical organ-specific autoimmunity such as a mother with thyroid or islet autoantibodies but not necessarily an autoimmune disease.

In most cases, overt diabetes is preceded by the presence of autoantibodies to islet antigens such as GADA, IAA, and IA-2A. This pre-clinical period, ranging from months to years, provides an opportunity for prevention. However, interventions applied after development of autoimmunity have been so far unsuccessful (Canadian-European Randomized Control Trial Group, 1988; DPT-1, 2002). Interventions initiated before the onset of autoimmunity and significant loss of insulin secretory capacity may be more effective, but may have to be applied in the first few years of life when pre-diabetic autoimmunity develops (Gale, 1996).

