#### 7. Screening procedures

#### 7.1. HLA typing

#### 7.1.1. HLA screening

Genotype screening will be performed using either a dried blood spot (DBS) punch or a small volume whole blood lysate (WBL) specimen format. Screening blood sample will be obtained generally at birth as a cord blood sample, but potential participants, especially first-degree relatives of T1DM patients can be screened using heel stick capillary sample up to the age of 4 months. This exception is made to maximize the number of newborn relatives participating in this study. The experience of the ongoing studies, such as DAISY and BABY-DIAB is that some families with a diabetic proband learn about those studies after

the baby is born, but are extremely interested in participation. These studies have also found that relatives are at a higher risk of T1DM than high-risk newborns from the general population, even stratifying for HLA-DR,DQ genotypes, and that these families are much less likely to drop out from prospective follow-up, thus particularly valuable to TEDDY. After PCR amplification of exon 2 of the HLA Class II gene (DRB1, DQA1 or DQB1), alleles will be identified either by direct sequencing, oligonucleotide probe hybridization, or other genotyping techniques. Additional typing to sufficiently identify certain DR-DQ haplotypes is as specified in Section 6.1 above.

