The following is a non-exhaustive listing of planned statistical analyses for the prospective part of the project:

- 1. We will classify infants as to whether or not they had early exposure to cereals or gluten in the diet (vs. those receiving only breast milk for the first 3 months). Those exposed will be compared to those not exposed using the Log Rank Test.
- Subjects will be classified, based on diet questionnaires, as consuming low or high levels of anti-oxidants such as carotenoids, ascorbic acid, and selenium. Those with low levels will be compared to those with high levels with respect to the development of T1DM and autoimmunity using Log Rank Tests.

- 3. Subjects' drinking water will be analyzed and subjects classified as drinking water with high or low concentrations of zinc, and nitrate and as low or high pH. Groups will be compared using the Log Rank Test.
- 4. Cox Regression will be used to study the association of the level of psychosocial stress with the development of T1DM and autoimmunity.

The following analyses will be performed in the nested case control portion of the study:

- The association between the number of enterovirus infections a child has and the development of T1DM and islet autoimmunity will be studied with Cox Regression. Using zero as the reference, dummy variables will be created to represent 1, 2, etc infections. The hazard ratios of these values relative to zero will be estimated and p values of the estimates computed. The same type of analyses will be done for the number of rotavirus infections.
- 2. Low levels of omega-3 fatty acids, EPA, and DHA in children's erythrocyte membranes have been associated with increased risk of islet autoimmunity. The odds ratio for each of these exposures will be estimated.
- 3. Low levels of alpha-tocopherol has been associated with increased risk of islet autoimmunity. The odds ratio for each of this exposure will be estimated

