## 10.5.2. Matching Criteria

As part of the study design of the case-control studies controls will be matched to cases on several confounding factors. This will be done to achieve a more statistically efficient analysis. The factors that are being considered as possibilities to match on are:

- HLA type
- Study center
- Duration of follow-up
- Completeness of data including serial biological samples
- Season of birth

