## **10.5.3. Statistical Considerations**

For the study of risk factors for the development of autoimmunity, those subjects developing autoimmunity will be cases and those not developing autoimmunity at that time will be controls (population density sampling). For each case, we will attempt to identify k controls (see below for considerations for the determination of k) that are matched to the case on study center, gender, and HLA type. Cost efficiency is achieved by determining the values of the laboratory parameters only for the cases and the chosen matched controls. We will then perform stratified

logistic regression using the matched sets as strata in order to study the effect of various possible risk factors, univariately and multivariately, on the odds of developing autoimmunity. Note that this analytic method does not require that every matched set contain exactly k controls. We can have varying numbers of controls for each case. Thus while we will attempt to have the same number of controls for each case, we will allow for fewer controls for cases with fewer matches and will choose more controls, to compensate, for those cases with more matches.

For the study of risk factors for the development of T1DM, we will consider those who developed T1DM by age 15 to be cases. For those who also developed autoimmunity as well, we will use the same controls as were chosen for the study of autoimmunity. The same analytic methods will be used.

The number of controls needed per case will depend, of course, on the number of cases and thus cannot be fully determined until the end of the planned follow-up periods. One plausible scenario, given in Table 14, assumes that for the pooled sample we would have 5.5% conversion by age 15 to diabetes among those exposed to a risk factor, that 20% would be exposed, that the hazard ratio for the risk factor is 2.0, and that 0% would be lost to follow-up. This would lead to about 460 cases.

The following tables presents the power for a case control study with 1-3 controls per case, odds ratio = 1.5 and 2.0, and 380 - 500 cases.

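### First-degree-relative status is not a matching factor, a stratum or a required covariate in the exposure analyses, although the protocol says it raises risk within HLA genotype

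*Protocol*

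**What the plan says.** **Matching.** The protocol describes it three times.

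- Section 10.1: "Matching will be based on HLA type, study center, duration of follow-up, and completeness of data including serial biological samples".
- Section 10.5.2 introduces its list with "The factors that are being considered as possibilities to match on are" and adds season of birth to the Section 10.1 factors.
- Section 10.5.3 speaks of controls "that are matched to the case on study center, gender, and HLA type".

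FDR status is in none of them.

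**Prospective tests.** For early cereal or gluten exposure, Section 10.1 says: "Those exposed will be compared to those not exposed using the Log Rank Test". The antioxidant and drinking-water items are also log-rank comparisons of two groups, with no stratification named. A continuous factor that shows non-proportional hazards is dichotomized and moved to a log-rank test. Cox and conditional logistic models are run with one factor and with several, without a named adjustment set. Section 10.3 gives power for the pooled sample (Tables 8 and 11) as well as for each group separately.

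**FDR status as a risk factor.** Section 7.1.1 cites the experience of ongoing studies: "relatives are at a higher risk of T1DM than high-risk newborns from the general population, even stratifying for HLA-DR,DQ genotypes". The same section reports better retention in families with an affected member. Section 10.3 adds: "Those from the general population and the relatives are expected to have about 4% and 13.3% autoimmune conversion at 6 years respectively". Its summary table uses the same two percentages for T1DM by age 15. Section 2 distinguishes by affected parent, comparing a diabetic father with a diabetic mother: "However, the risk of the child developing the disease is higher when born to a T1DM father".

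**The concern.** FDR status predicts the outcome, and on the protocol's own statement HLA matching does not remove this. If an exposure is also more or less common in relatives, FDR status confounds its association with autoimmunity or T1DM. Pregnancy factors, infant feeding, supplements and stress are plausible candidates, although the protocol gives no exposure prevalence by FDR status.

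Matching on HLA and center leaves relatives over-represented among cases compared with their controls. A pooled two-group log-rank test has no protection at all. The rule that sends non-proportional continuous factors to a log-rank test takes those factors out of the only framework in which adjustment could occur. At stake are the nominal 1% error rate and the reading of modest hazard or odds ratios, in a study that powers for ratios of 1.5 and 2.0.

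**Working it through.** **Inputs.** Enrollment by center is from Table 5: 7,013 general-population children and 788 relatives. Planning risks of 4% and 13.3% are from Section 10.3. Counselling risks of 1 in 20 and 1 in 12 are from Section 7.1.3. Alpha is 0.01 two-sided. Exposure prevalences, eG in general-population children and eF in relatives, are assumptions.

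**1. The plan's case numbers reproduce.** 7,013 × 0.04 = 280.5 (stated 281) and 788 × 0.133 = 104.8 (stated 105). Relatives are 788/7,801 = 10.1% of the cohort and 104.8/385.3 = 27.2% of cases.

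**2. Size of the FDR effect.** The planning risk ratio is 13.3/4 = 3.3, and the hazard ratio is ln(0.867)/ln(0.96) = 3.5. The counselling risk ratio is (1/12)/(1/20) = 1.67. Both are crude.

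**3. Share of relatives among center-matched controls.** Cases per center are 0.04 × G + 0.133 × F, where G and F are general-population children and relatives enrolled. A control drawn from that center is a relative with probability F/(G+F).

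| Center | G | F | Cases | Relatives among cases | Relatives in cohort |
|---|---|---|---|---|---|
| Colorado | 1,312 | 113 | 67.5 | 22.3% | 7.9% |
| Finland | 1,384 | 127 | 72.3 | 23.4% | 8.4% |
| Georgia/Florida | 699 | 57 | 35.5 | 21.3% | 7.5% |
| Germany | 327 | 236 | 44.5 | 70.6% | 41.9% |
| Sweden | 2,122 | 118 | 100.6 | 15.6% | 5.3% |
| Washington | 1,169 | 137 | 65.0 | 28.0% | 10.5% |

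The case-weighted mean of the last column is 11.6%, against 27.2% of cases. At the counselling risks the two shares are 10.6% and 15.8%.

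**4. Odds ratio for a null exposure, center-matched.** Exposure prevalence is eG + (eF − eG) × (share of relatives).

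- Planning rates, 10% vs 30%: cases 0.10 + 0.20 × 0.272 = 0.154, controls 0.10 + 0.20 × 0.116 = 0.123, OR 1.30.
- Planning rates, 10% vs 20%: 0.127 and 0.112, OR 1.16.
- Counselling rates: OR 1.10 (10% vs 30%) and 1.05 (10% vs 20%).

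The 1:1 discordant-pair calculation within centers gives the same values. At the planning rates, rejection at 1:1 is about 9% (10% vs 30%) and 3% (10% vs 20%).

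**5. Pooled, unstratified log-rank for a null exposure.** For 10% vs 30% at the planning rates:

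- Relatives among the exposed: 0.101 × 0.30 / (0.101 × 0.30 + 0.899 × 0.10) = 25.2%. Among the unexposed: 8.0%.
- Risks: 0.252 × 0.133 + 0.748 × 0.04 = 6.34%, and 4.75%.
- Crude HR: ln(1 − 0.0634)/ln(1 − 0.0475) = 1.35.

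The rejection rates below come from simulation with exponential event times, 15 years of follow-up and no losses. A Schoenfeld approximation gives lower values at the planning rates: 6% and 25%.

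| Null exposure (general population vs relatives) | Planning rates: crude HR, rejection | Counselling rates: crude HR, rejection |
|---|---|---|
| 10% vs 20% | 1.18, about 7 to 8% | 1.06, about 2% |
| 10% vs 30% | 1.35, about 33% | 1.11, about 4% |

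At the planning rates, 10% vs 15% gives HR 1.09 and about 2% rejection. An exposure rarer in relatives (10% vs 5%) gives HR 0.90 and so looks protective.

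**6. After the change.** Stratifying the same simulated log-rank tests by FDR status brings rejection back to about 1% in every setting.

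**The case against.** The strongest reply is that family history is not ignored. Section 10.1 names it as a factor for log-rank study, reports multivariate models beside single-factor ones, and intends to look into confounding and effect modification. Section 10.3 gives power for relatives and general-population children separately (Tables 6, 7, 9 and 10). Both interim power tables are for the general population only, and the second secondary objective in Section 4 compares determinants by FDR status. The Section 10.5.2 list is tentative, and the list of prospective analyses is described as incomplete. A reader might infer that FDR status plays no part in the analysis, and the documents do not support that. What remains is that studying family history as an exposure does not adjust other exposures for it. Where the protocol does fix matching factors and tests, it fixes them without FDR status. That an SAP might name covariates does not repair the matching lists or the plain log-rank tests.

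A reader might also infer that FDR status triples risk within HLA type. No within-HLA ratio is given. The 3.3 compares different eligibility sets: four genotypes with DRB1*0403 excluded for the general population, ten without DR4 subtyping for relatives. The counselling figures give 1.67.

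Nor will every exposure that differs by FDR status look like a trigger. Small prevalence gaps do little, and the bias can run the other way. No such gap is documented: the infant behavior-change data in Section 8.12.4.3.3 concern mothers of genetically at-risk infants, not relatives compared with other families.

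Finally, controls must have complete data, and relatives are said to drop out less, so relatives may be more common among controls than 11.6%. HLA matching on the genotypes open only to relatives works the same way. Both points stand and would reduce the matched odds ratios above.

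**Conclusion.** The point holds in limited form. FDR status is not a matching factor, a stratum in the listed log-rank exposure tests, or a required covariate, although the protocol itself says it carries risk beyond HLA genotype. Pooled and single-factor results for exposures that differ markedly by FDR status can therefore be spurious in either direction.

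The size depends on two things the documents do not settle: the within-HLA risk ratio and the exposure gap. Under the assumed gaps, the pooled test's error rate runs from about 2% (counselling risks, 10% vs 20%) to about 33% (planning risks, 10% vs 30%), against a nominal 1%. The matched odds ratio runs from 1.05 to 1.30. The multivariate models and separate power tables reduce the problem, but they do not oblige anyone to adjust.

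**What to change.** - Stratify every pooled log-rank and Cox exposure analysis by FDR status, including the log-rank tests used when proportional hazards fails. Split by affected relative (mother, father, sibling) only where numbers allow.
- Include FDR status in every conditional logistic model, including the single-factor ones.
- Do this by adjustment rather than by adding FDR status to the matching. Hypothesis 2, which compares relatives with general-population children given HLA and exposure, then remains estimable in the case-control sets.

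This is a free improvement. The variable is known at enrollment, no new data are needed, and the cost is about one degree of freedom per model, or up to three if affected relatives are separated.
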